# 11.5. TREATMENT PERIOD

Treatment visits (n = 8) will be at week 2 (visit 2) and every 2 weeks until week 16 (visit 9). A follow-up visit will be performed at week 20. Visits will be organised in the outpatient clinic preferably with the same physician investigator in collaboration with a study nurse for investigational drug administration. The duration of the visits will be of 30 to 45 minutes. All appointments will be planified at day 0 and the patient will be provided with a full study schedule.

At study treatment stop (as per protocol or in case of premature stop), Asthmatic patients must be closely monitored: the investigator will assess the asthma and will decide to direct the patient to his pulmonologist if necessary. The patient will be informed about the necessity of consulting quickly in case of recurrence of asthmatic symptoms and as a matter of urgency in case of asthma crisis.

At each visit, in case of persistent conjunctivitis, not recovered with standard treatments, investigator will send the patient to a referent ophthalmologist of his establishment.

#### Visit 2/ Week 2:

The treatment allocated (dupilumab or placebo) will be administered at home (self\_injection) or at site (by site staff) according to patient's preference.

#### Visit 3/ Week 4:

The following information will be collected:

- Concomitant medications and procedures
- AEs and AESI (Conjunctivitis)

The following procedures/assessments will be conducted by the investigator or designee:

- mTLSS,
- EASI (if applicable)
- IGA.
- PGA,
- DLOI,
- EO-5D,
- Hand eczema Pruritus VAS,
- Hand eczema Pain VAS,
- Hand eczema Sleep loss VAS.

The treatment allocated (dupilumab or placebo) will be administered.

#### Visit 4/ Week 6:

The treatment allocated (dupilumab or placebo) will be administered at home (self\_injection) or at site (by site staff) according to patient's preference.

#### Visit 5/Week 8:

The following informations will be collected:

- Concomitant medications and procedures
- AEs and AESI (Conjunctivitis)

The following procedures/assessments will be conducted by the investigator or designee:

- mTLSS,
- EASI (if applicable)
- IGA,
- PGA,
- DLQI,
- EQ-5D,
- Hand eczema Pruritus VAS,
- Hand eczema Pain VAS,
- Hand eczema Sleep loss VAS,
- Photographs of the hands,
- Urinary pregnancy test if applicable.

The treatment allocated (dupilumab or placebo) will be administered.

Visit 6/ Week 10:

The treatment allocated (dupilumab or placebo) will be administered at home (self\_injection) or at site (by site staff) according to patient's preference.

#### Visit 7/Week 12:

The following informations will be collected:

- Concomitant medications and procedures
- AEs and AESI (Conjunctivitis)

The following procedures/assessments will be conducted by the investigator or designee:

- mTLSS,
- EASI (if applicable)
- IGA,
- PGA,
- DLQI
- EO-5D-5L
- Hand eczema Pruritus VAS,
- Hand eczema Pain VAS,
- Hand eczema Sleep loss VAS,
- Urinary pregnancy test (if applicable).

The treatment allocated (dupilumab or placebo) will be administered.

#### Visit 8/Week 14:

The treatment allocated (dupilumab or placebo) will be administered at home (self\_injection) or at site (by site staff) according to patient's preference.

#### Visit 9/ Week 16:

The following information will be collected:

- Concomitant medications and procedures
- AEs and AESI (Conjunctivitis)

The following procedures/assessments will be conducted by the investigator or designee:

- mTLSS,
- IGA,
- EASI if applicable,
- PGA,
- DLQI,
- EQ-5D-5L,
- Hand eczema Pruritus VAS,
- Hand eczema Pain VAS,
- Hand eczema Sleep loss VAS,
- WPAI questionnaire,
- Photographs of the hands,
- Laboratory samples:
  - o Full blood count including Eosinophils
  - Serum Chemistry
  - o Serum hCG for women of child-bearing potential
  - o Total IgE
  - o Specific IgE

Asthma will be assessed for concerned patient. The investigator will decide to direct the patient to his pulmonologist if necessary.

# 11.6. FOLLOW UP VISIT (END OF STUDY VISIT)

Follow up visit will take place at week 20. It will consist in:

- collecting concomitant medications
- collecting adverse events and AESI (Conjunctivitis)
- Urinary pregnancy test if applicable.

Asthma will be assessed for concerned patient. The investigator will decide to direct the patient to his pulmonologist if necessary.

#### 11.7. RULES FOR INTERRUPTING THE STUDY

The end of the study does correspond to the end of study participation.

In line with the current regulation, each patient can at any time withdraw from the study. The participation to this study is voluntary. The patient does not have to provide with any justification for withdrawing his/her participation. If a patient stops the treatment during the study, if he wants, he'll be followed in the study.

The investigator will have to complete an early termination visit sheet in the CRF indicating the reason for interruption of the study: premature discontinuation (efficacy/safety issue), lost to follow-up, withdrawal of consent, major deviation from the protocol.

The subject withdrawing prematurely from the study will not be replaced.

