# 11. STUDY PROCEDURE

# 11.1. STUDY CALENDAR

The duration of the study for each patient will be between 21 and 24 weeks and will comprise three phases:

- A screening phase with a duration of 1 to 4 weeks
- A treatment phase with a duration of 16 weeks (4 treatment visits with injection, 4 self-injection at home or 4 injections at site by study staff and end of treatment visit)
- A post treatment follow-up phase with a duration of 4 weeks (follow up visit planned 6 weeks after the last injection and 4 weeks after the end of treatment visit)

The inclusion of the first patient happened in July 2019. The inclusion period is 54 months.

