### 13.3. SUBJECT POPULATIONS FOR ANALYSIS

- The Intention-to-Treat (ITT) population will consist of all randomized patients, independently of whether they receive study treatment or not. Patients will be analysed according to the treatment they were randomised to receive and not according to what they actually received, if different.
- The Per Protocol (PP) population will consist of all randomised patients who are evaluable for primary endpoint and who are considered not to have major protocol deviations (e.g. violation of major eligibility criteria, non-compliance to randomised treatment, use of forbidden drug...). The major protocol violations are patients who do not fulfill the diagnosis criteria for hand dermatitis, patients who have only mild disease at baselines or patients who use systemic immunosuppressants including oral corticosteroids during the study. The major protocol violations will be further defined in the SAP and validated by the coordinating investigator of the study.
- The Treated population will include all randomised patients who receive at least one dose of the study treatment (dupilumab or placebo). Subjects will be analysed according to the actual treatment received.

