## Primary efficacy endpoint analysis

In primary efficacy analysis, the percentage change in mTLSS score from baseline to Week 16 will be compared between both groups using a covariance analysis including the group, the stratification factor (personal history of atopy) and the baseline mTLSS score as covariables. Treatment effect will be tested at a 5% significance level (confirmatory test). The ITT population will be used for this primary efficacy analysis. Missing data on mTLSS score at Week 16 will be replace using the Last-Observation-Carry-Forward (LOCF) imputation method.

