## Sensitivity analyses on primary efficacy endpoint

Three sensitivity analyses will be performed. In the first, multiple imputations method will be used to handle missing outcomes. In the second, no imputation of missing data will be done meaning that only patients evaluable for primary endpoint among the ITT population will be considered in the analysis. Finally, the efficacy analysis will be done on the Per-Protocol population.

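### Section 11.7 leaves follow-up after stopping treatment optional and the protocol names no mTLSS at early exit, so a missing Week 16 primary outcome may rest on a value four or more weeks old

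*Protocol*

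**What the plan says.** Protocol section 11.7 distinguishes stopping treatment from leaving the study, and lets patients who stop remain: "If a patient stops the treatment during the study, if he wants, he'll be followed in the study". It then asks the investigator for an "early termination visit sheet in the CRF indicating the reason for interruption of the study" and lists the reasons as "premature discontinuation (efficacy/safety issue), lost to follow-up, withdrawal of consent, major deviation from the protocol". The reason is the only content that the protocol names for that sheet.

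Section 11.1 describes the treatment phase as "4 treatment visits with injection, 4 self-injection at home or 4 injections at site by study staff and end of treatment visit". The schedule in 11.2 marks mTLSS at Day 0 and Weeks 4, 8, 12 and 16 only, and it has no early-termination column. The visit text in 11.5 gives Weeks 2, 6, 10 and 14 an injection and no efficacy measure. The Week 20 visit in 11.6 has no mTLSS. Section 11.5 does foresee a premature treatment stop, but what it asks for then is an asthma assessment.

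On the analysis side, section 13.3 says the ITT population "will consist of all randomized patients, independently of whether they receive study treatment or not". Section 13.4 makes ITT the primary population and adds: "Missing data on mTLSS score at Week 16 will be replace using the Last-Observation-Carry-Forward (LOCF) imputation method". The sensitivity analyses are multiple imputation, a per-protocol analysis, and one without imputation in which "only patients evaluable for primary endpoint among the ITT population will be considered in the analysis".

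**The concern.** An ITT comparison at Week 16 needs a Week 16 measurement on as many randomised patients as possible, including those who stopped the drug. Section 11.7 permits that measurement without asking for it. Its list of reasons also gives a site an easy route to closing a patient's participation after an efficacy or safety stop, or after a deviation.

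The patients concerned may differ by arm and by outcome. Section 9.2 allows one two-week rescue course of topical corticosteroid and otherwise bars topical corticosteroids, topical calcineurin inhibitors and, with a narrow exception, systemic immunosuppressants. Section 13.3 counts systemic immunosuppressant use as a major violation, and 11.7 lists major deviation as a reason for interruption. A patient who flares again and needs systemic treatment therefore fits a listed exit reason. If dupilumab works as hypothesised, that could happen more often on placebo.

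For such a patient without a Week 16 visit, the primary outcome is a carried value. The analysis without imputation and the per-protocol analysis leave the patient out. Multiple imputation can use the Week 4, 8 and 12 scores, but it still models an outcome nobody observed. An SAP can choose how to impute; it cannot create the measurement.

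**Working it through.** **Planned size (13.1).** Difference 25 points, SD 40, two-sided 5%, t-test. The requirement is 41.2 per arm, so 42, with power 80.8%. Inflation: 84 / (1 − 0.10) = 93.3, so 94, or 47 per arm. The plan's figures reproduce. The allowance is 94 − 84 = 10 patients, and 10/94 = 10.6%.

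**Age of the carried value.** Age = 112 days minus the day of the last scheduled mTLSS. The range applies the ±3-day window to the carried visit.

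| Last scheduled mTLSS | Age at nominal Day 112 | Range |
|---|---|---|
| Week 12 (Day 84) | 112 − 84 = 28 days | 25–31 |
| Week 8 (Day 56) | 112 − 56 = 56 days | 53–59 |
| Week 4 (Day 28) | 112 − 28 = 84 days | 81–87 |
| Day 0 only | 112 days | percent change set to 0 |

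If the Week 16 window is also allowed to vary, the Week 12 value is 22 to 34 days old.

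**Effect on an arm mean.** Each patient carries 1/47 = 2.1% of the mean. An error of 10 points in one carried value (assumed) moves it by 10/47 = 0.21 points. If all 10 allowed patients fell in one arm and erred by 10 points in the same direction, the shift would be 10 × 10/47 = 2.1 points, against a 25-point target. If errors balance between arms, the net shift is about zero.

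**Effect on power (illustration).** Assume 47 per arm, SD 40, a share d of each arm carried forward, and carried values that keep a fraction f of the effect. The expected difference is 25 × [1 − d × (1 − f)].

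| d | f | Difference | Power |
|---|---|---|---|
| 0 | – | 25.0 | 85.0% |
| 10% | 0 | 22.5 | 77.0% |
| 10% | 0.50 | 23.75 | 81.3% |
| 10% | 0.75 | 24.4 | 83.2% |
| 20% | 0 | 20.0 | 66.9% |
| 20% | 0.50 | 22.5 | 77.0% |
| 20% | 0.75 | 23.75 | 81.3% |

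**Reach of a change now.** Inclusion began in July 2019 for 54 months (11.1), and version 6.0 is dated June 26, 2023. Elapsed time is 46.9 to 47.8 months, which leaves 6.2 to 7.1. With even accrual (assumed), 94/54 = 1.74 patients per month, so 10.8 to 12.4 are still to enrol. Patients inside their 16 weeks (3.68 months) number 1.74 × 3.68 = 6.4. The total is about 17 to 19 of 94, or 18% to 20%.

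**The case against.** The strongest reply is that the protocol already does much of what is asked.

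- **No one is sent home.** Patients who stop drug may stay on the same schedule, and participation is voluntary under any wording. A reader might infer that the listed reasons order removal from the study. The text does not say so: it tells the investigator what to record.
- **Treatment stop is an interpretation.** The first listed reason does not say of what. Because loss to follow-up and withdrawn consent are listed separately, treatment stop is the most natural reading, but leaving the study for those reasons is possible.
- **An exit mTLSS may exist.** The sheet is called a visit sheet and the CRF is not shown. A reader might infer that mTLSS is omitted at exit. The protocol is only silent, and nothing forbids an unscheduled score.
- **Dosing is already recorded.** Sections 8.2.1 and 8.2.2 provide traceability logs and an eCRF administration page, and 12.3 records the action taken for each adverse event. What is not named is a reason for stopping treatment, kept apart from the reason for leaving the study.
- **Harm is not shown, and multiple imputation is planned.** Both are true. At the 10% allowance, power falls below 80% only in the illustrated case where carried values keep none of the effect.

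These replies limit the point to a default left unset and an exit measure left unnamed. They do not answer it: a permission to stay gives sites no reason to ask, and sites may differ in what they collect at exit.

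**Conclusion.** The point holds in a limited form and is worth fixing. Section 11.7 makes post-treatment follow-up optional and lists a deviation, and what is most naturally a treatment stop, as reasons for interrupting the study. With no mTLSS named at exit, a missing Week 16 value in the ITT primary analysis comes from a scheduled score nominally 28 days old or more, unless the early termination sheet supplies a later one.

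A reader might infer that the primary result is biased towards or away from dupilumab. The document does not support either: size and direction are unknown, and at the planned 10% rate the effect is likely modest. The power figures rest on assumed shares of carried patients and retained effect. A 20% loss would be worse, but the protocol does not anticipate it.

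**What to change.** Main change, in section 11.7:

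1. State that patients who stop treatment or have a protocol deviation stay in the study and are asked to attend the scheduled visits through Week 16 (mTLSS and the other efficacy measures) and Week 20 (safety), unless they withdraw consent or are lost to follow-up.
2. Remove major deviation as a reason for ending participation.
3. Record the reason for treatment stop separately from the reason for study exit. Dosing dates are already logged.

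Secondary step: name a dated mTLSS on the existing early termination sheet for patients who do leave. Its gain under LOCF is small. An exit at Week 6 would give a value 10 weeks old in place of the Week 4 value at 12 weeks.

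Cost: amendment wording and a CRF change, with N unchanged at 94 and the Week 16 and Week 20 visits already scheduled. If the amendment is substantial, section 16 requires ethics committee approval and ANSM authorisation first, and a new consent form if constraints change. It reaches about 17 to 19 patients, fewer after approval time; at a 10% rate that is about two with a missing Week 16 value. The trial would then hold two follow-up rules, and Week 16 values measured after other therapy would need flagging. Patients may still decline visits. The per-protocol set may still exclude early stoppers, because section 13.3 counts non-compliance with the randomised treatment as a major deviation.

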#### 11.8. CONSTRAINTS RELATING TO THE STUDY

Patients included in this study can not participate simultaneously in another investigational drug study for the entire study duration. Participation of patients is voluntary and no monetary compensation will be provided.

#### 11.9. COLLECTION OF BIOLOGICAL SAMPLES

Patients included in the centers of Lyon and Toulouse will be proposed to participate to an optional pathophysiology sub-study to understand the mechanism of action of dupilumab. For this sub-story,

A biological collection will be realized with residual material after analysis (cutaneous biopsy, extracted ARN) to perform additional analyses (confirmation of a result for example) if needed. Biologic samples will be retained at UDEAR Inserm U1056, Toulouse Purpan Hospital .

# 12. MANAGEMENT OF ADVERSE EVENTS AND NEW FACTS

# 12.1. DEFINITIONS

#### **Adverse Event** (Article R1123-46 of the Public Health Code)

Any harmful manifestation occurring in a participant in a research study that involves the human person, whether or not the event is related to the research or product to which the research relates.

#### **Adverse reaction** (Article R1123-46 of the Public Health Code)

Any adverse event occurring in a participant in a research study that involves the human person, when this event is related to the research or product to which the research relates.

**Serious adverse reaction or event** (Article R1123-46 of the Public Health Code and ICH-E2B guideline) Any adverse reaction or event that:

- ✓ results in death,
- ✓ endangers the life of the participant,
- ✓ requires hospitalisation or prolongation of hospitalisation,
- ✓ causes an inability or significant or long-term disability,
- ✓ results in an abnormality or congenital malformation,
- ✓ or any event considered to be medically serious,

and with respect to the drug, regardless of the dose administered.

The expression "life-threatening" is reserved for an immediate life threat at the time of the adverse event.

# **Unexpected adverse reaction** (Article R1123-46 of the Public Health Code)

- Any adverse reaction to the product including the nature, severity, frequency or outcome of which is inconsistent with the safety reference information referred to in the Summary of Product Characteristics or in the investigator's brochure when the product is not authorised. In this protocol, the safety reference information is represented by IB v.12 (4-Apr-2018).

#### **New fact** (Article R1123-46 of the Public Health Code)

- Any new data that may lead to a reassessment of the risk to benefit ratio of the research or of the product being researched, changes in the use of this product, in the conduct of the research, or to the documents relating to the research, or data that may lead to the suspension, discontinuation or modification of the research protocol or similar research.

**Intensity/severity:** the table below will be used for AE severity grading.

Severity	Description
GRADE 1 – Mild	Transient or mild discomfort; no limitation in activity; no
	medical intervention/therapy required.
GRADE 2 – Moderate	Mild to moderate limitation in activity—some assistance
	may be needed; no or minimal medical
	intervention/therapy required.
GRADE 3 – Severe	Marked limitation in activity, some assistance usually
	required; medical intervention/therapy required
	hospitalizations possible.
GRADE 4 – Life-threatening	Extreme limitation in activity, significant assistance
	required; life-threatening (immediate risk of death);
	significant medical intervention/therapy required,
	hospitalization or hospice care probable.
GRADE 5 – Fatal	Death

#### 12.2. DESCRIPTION OF EXPECTED SERIOUS ADVERSE EVENTS

The serious adverse events expected in the context of this protocol are listed here:

- related to the study treatment (dupilumab): rare hypersensitivity reaction, eyes disorders (severe conjunctivitis or keratitis for example), injection site reaction, herpes infection, hypereosinophilia.
   Other expected adverse events related to dupilumab are described in reference document (IB v.12 (4-Apr-2018)).
- related to the study procedures (blood tests, questionnaires) : none related to evolution of the disease: relapse, flair of hands eczema
  - related to skin biopsy (performed in optional sub-study): skin biopsy may lead to pain, edema, located bleeding, cutaneous infection or healing issue (healing delay, persisting scar...).

Any serious adverse reaction reported in this study will be considered as "unexpected" (SUSAR) if it is not listed in section 10.2 of the protocol or in IB v.12 (4-Apr-2018) of dupilumab.

#### 12.3. ACTION TO BE TAKEN IN THE CASE OF AN ADVERSE EVENT OR NEW FACT

#### Adverse events collection:

Participating investigators will assess the occurrence of AEs and SAEs at all participant evaluation time points during the study.

All AEs and SAEs whether reported by the participant, discovered during questioning, directly observed, or detected by physical examination, laboratory test or other means, will be recorded in the participant's medical record and on the appropriate study-specific case report forms. All AEs must be recorded in the participant's medical record, stating the duration of the event, action taken by the investigator and outcome of the event. The investigator must evaluate the causal relationship between the study drug and the AE.

#### Exception to collection:

The following circumstances will not be collected:

- admission for social or administrative reasons,
- hospitalisation predefined by the protocol,
- hospitalisation for scheduled medical or surgical treatment prior to the research,

#### **Adverse events of special interest**

Conjunctivitis will be considered as adverse events of special interest (AESIs) in this trial and must be reported as serious adverse events even if there is no seriousness criteria.

It will require additional details to be recorded in the eCRF. Sponsor may request that the investigator forward complementary information, as appropriate.

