#### 3.4. BENEFIT/RISK RATIO

Dupilumab has been approved in the USA and in EU for use in moderate to severe atopic dermatitis when systemic treatment is indicated. The foreseeable benefits are clearance or almost clearance of hand eczema in about 40% of patients and 75% improvement in the severity score in 50 to 70% of patients at 16 weeks. The foreseeable risks are according to the dupilumab US label:

- Hypersensitivity (rare)
- The occurrence of eye related disorders (conjunctivitis, keratitis, blepharitis, eye pruritus)
- Oral herpes or other herpes simplex virus infection
- Injection site reactions
- Initial increase from baseline in eosinophil count

The anticipated benefit-risk ratio of dupilumab for the treatment of moderate to severe CHE appears to be highly favorable.

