#### CONCOMITANT MEDICATIONS / ADVERSE EVENT (AE)

Any medication or vaccine that subject receives from 3 months priori screening through safety follow up must be recorded in the subject's medical record and the eCRF along with the details such as: reason for use, dates of administration (start and stop date), dosage information (dose and frequency). Similarly, concomitant procedures must also be recorded in the subject's medical record and the eCRF.

AEs must be collected from time of first trial-related activity after the subject has signed the informed consent form until completion of the clinical trial. AEs must be assessed by medically qualified personnel. AEs reported by the subject or observed by the investigator must be recorded on the AE form of the CRF and should be described.

AESI (Conjunctivitis) must be recorded in the eCRF and reported immediately to the Sponsor (see.section 10.3).

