## **Serious adverse events notification:**

The investigator must immediately notify the sponsor on the day that he becomes aware of it of any serious adverse event or any new fact or pregnancy, if it occurs:

- after the date of signature of the consent form,
- at any time during the period of follow-up planned by the study for the participant,

If the investigator becomes aware of a serious adverse event, which he/she suspects is causally related to the research, occurring after the end of the clinical trial in a participant he/she has treated, he/she shall inform the sponsor without delay.

TYPE OF EVENT	NOTIFICATION METHOD	TIME LIMIT FOR NOTIFYING THE SPONSOR
Non-serious AE	In the case report form	No immediate notification
AE of special interest (conjunctivitis)	In the case report form + initial SAE declaration form	Sponsor to be notified immediately
SAE	Initial SAE declaration form + written report if necessary	Sponsor to be notified immediately
New fact	Declaration form + written report if necessary	Sponsor to be notified immediately
Pregnancy	Pregnancy declaration form	On confirmation of the pregnancy

Name of sponsor/Vigilance Unit: CHU de Toulouse [name] [name] [contact]

*E-mail*: [contact]

All these events must be monitored until they are **completely resolved**. The investigator will send the sponsor additional information (additional declaration form) concerning the evolution of the event not mentioned in the initial report.

The investigator and the sponsor must evaluate the causal relationship between the study drugs (dupilumab/placebo) and the SAE, independently. If the SAE is not related to the study drug, the investigator and the sponsor must determine the alternative causality (eczema, concomitant treatment, other pre-existing disease, etc...). If they are not agreed about the final causality assessment, this discrepancy has to be notified in the SAE report.

All SAE that are considered to be reasonably related to the IMP, will be defined as a "serious suspected adverse reaction".

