#### **Pregnancies**

Pregnancy occurring during the period or immediately after a study does not constitute an SAE. However, a pregnancy must be notified in the same way as an SAE because it requires particular monitoring throughout its duration. In the event of pregnancy, dupilumab should be immediately discontinued and the pregnancy must be reported immediately of the Investigator's knowledge of it by fax to the Sponsor using the Pregnancy Reporting Form.

The Investigator will follow the female subject until completion of the pregnancy, and must notify the Sponsor of the outcome of the pregnancy immediately when having knowledge of the outcome using the Follow-Up Pregnancy Reporting Form.

Any anomaly observed in the foetus or child will then be notified. Any elective termination of pregnancy (ETP), medical termination of pregnancy (MTP) or spontaneous abortion must give rise to a notification of pregnancy, and if it necessitated hospitalisation, it must be passed on in the same manner as an SAE.

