## Safety analysis

The percentage of patients reporting the occurrence of treatment emergent adverse events classified by MedDRA System Organ Class (SOC) and Preferred Term (PT) will be presented by group with exact 95% Confidence Interval (CI) from study start to study end (Week-20 visit). No statistical test will be performed to compare incidences between groups due to the lack of power and issues with multiplicity testing.

The same table will be provided for adverse events of severe intensity and for adverse events related to study treatment.

The overall percentage of patients reporting at least one adverse event and at least one serious adverse event will also be computed with exact 95% CI.

All serious adverse events will be detailed in listings with start date, duration in days, intensity, causality assessment, action taken, outcome and dates of first and last study treatment administration.

The overall percentage of patients reporting injection site reactions will also be presented by group with exact 95% CI together with the evolution at 16 weeks since baseline of laboratory parameters (full blood count, transaminases, total IgE and specific IgE).

Safety analyses will be done on the treated population.

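### Conjunctivitis must be reported as an SAE even when no seriousness criterion is met, and the safety analysis does not say which meaning of SAE it counts; the descriptive SAE percentage and listing may be inflated

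*Protocol*

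**What the plan says.** **Definition.** Section 12.1 defines a serious event by criteria: death, threat to life, hospitalisation, disability, congenital malformation, and a residual category, "or any event considered to be medically serious".

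**Rule for conjunctivitis.** Section 12.3 (Adverse events of special interest) says that conjunctivitis "must be reported as serious adverse events even if there is no seriousness criteria". In the notification table of the same section, the special-interest row gives the method as "In the case report form + initial SAE declaration form", with immediate notice to the sponsor. Section 11.4 says "AESI (Conjunctivitis) must be recorded in the eCRF and reported immediately to the Sponsor" and does not call the event serious.

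**Contrast with pregnancy.** Section 12.3 (Pregnancies) says expressly that a pregnancy is not an SAE, although "a pregnancy must be notified in the same way as an SAE".

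**Analysis.** Section 13.4 (Safety analysis) says that the "percentage of patients reporting at least one adverse event and at least one serious adverse event will also be computed", with an exact 95% interval, and that all SAEs will be listed. The listing fields are start date, duration, intensity, causality, action taken, outcome and dosing dates. The seriousness criterion is not among them.

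**Direction.** Section 3.4 includes among the foreseeable risks of dupilumab "The occurrence of eye related disorders (conjunctivitis, keratitis, blepharitis, eye pruritus". Section 12.2 gives severe conjunctivitis as an example of an expected serious event related to dupilumab. Neither section gives a rate.

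**The concern.** The protocol uses SAE in two ways. In 12.1 it is an event that meets a criterion. In the conjunctivitis rule it also covers an event that, by the rule's own words, meets none. Section 13.4 then counts and lists SAEs without choosing between them, so two competent analysts could produce different SAE percentages from the same data.

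The difference would probably not be neutral between arms. If conjunctivitis is more frequent on dupilumab, as 3.4 and 12.2 suggest, counting non-serious cases would raise the dupilumab SAE percentage more than the placebo one. Safety against placebo is a stated secondary objective (4.2). Because 13.4 plans no between-group test on safety, readers will judge from the percentages and their intervals, which is where the distortion would appear.

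**Working it through.** **1. Is there a conflict in the text?**

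- The residual category in 12.1 does not remove it. One could suppose that the protocol treats every conjunctivitis as medically serious, but the rule covers cases with no seriousness criterion, and being medically serious is itself one of the criteria.
- The pregnancy paragraph separates how an event is notified from what it is. The conjunctivitis paragraph does not. It says the event is reported as an SAE, with no statement that it remains outside the class.
- Section 13.4 uses the term without a qualifier, so it inherits the ambiguity.

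**2. Is there a stated figure to reproduce?** No. The protocol gives no SAE or conjunctivitis rate for either arm. The only usable input is the planned total of 94 randomised 1:1 (13.1), that is 94 / 2 = 47 per arm. This takes all randomised patients as treated, since safety is analysed in the treated population. Everything below is illustration on assumed rates.

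**3. Illustration by rates.** Let s be the true SAE probability, equal in both arms, and c the probability of non-serious conjunctivitis, independent of other SAEs. If every conjunctivitis is counted, the reported probability is 1 − (1 − s)(1 − c).

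| s | c dupilumab / placebo | Reported dupilumab | Reported placebo | Artificial difference |
|---|---|---|---|---|
| 2% | 5% / 2% | 1 − 0.98 × 0.95 = 6.9% | 1 − 0.98 × 0.98 = 4.0% | 2.9 points |
| 2% | 10% / 3% | 1 − 0.98 × 0.90 = 11.8% | 1 − 0.98 × 0.97 = 4.9% | 6.9 points |
| 2% | 20% / 5% | 1 − 0.98 × 0.80 = 21.6% | 1 − 0.98 × 0.95 = 6.9% | 14.7 points |
| 4% | 5% / 2% | 8.8% | 5.9% | 2.9 points |
| 4% | 20% / 5% | 23.2% | 8.8% | 14.4 points |

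The true difference is 0 in every row.

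**4. Illustration by counts**, with exact (Clopper-Pearson) 95% intervals and one true SAE per arm:

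- Counting only events that meet a 12.1 criterion: 1/47 = 2.1% (0.1 to 11.3) in each arm.
- Adding 5 dupilumab patients and 1 placebo patient whose only event is non-serious conjunctivitis: 6/47 = 12.8% (4.8 to 25.7) against 2/47 = 4.3% (0.5 to 14.5).
- Adding 2 to 7 such patients on dupilumab: from 3/47 = 6.4% (1.3 to 17.5) to 8/47 = 17.0% (7.6 to 30.8).

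**The case against.** The best defence is that the rule only sets a notification route. It sits in the section on action to be taken, and its closing clause accepts that the event may not be serious. The notification table has separate rows for non-serious events, events of special interest and SAEs; if every conjunctivitis were an SAE, the middle row would be redundant. Section 11.4 asks only for recording and immediate reporting. On this reading 12.1 remains the sole definition, 13.4 uses it, and no non-serious case enters the SAE percentage. The SAP, which is not shown, could say so.

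Much of this stands. The notification-only reading is reasonable, perhaps the intended one, and inflation is therefore a risk and not a certainty. It does not dispose of the point, because the difficulty is more than silence left for a SAP: the rule is an affirmative statement at odds with 12.1, and the pregnancy paragraph shows that the disclaimer could have been written.

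A reader might infer more than the protocol supports:

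- *That the SAE rate will be inflated.* This depends on which reading the analyst takes and on rates that the protocol does not give.
- *That an excess could not be told apart from real serious harm.* The listing shows intensity, causality, action taken and outcome for each event, and 12.3 requires extra eCRF detail for conjunctivitis. In the count illustration at most 8 dupilumab patients would be listed. A reader could separate most cases, although not from a seriousness field.
- *That conjunctivitis goes unreported by arm.* Section 13.4 tabulates treatment-emergent events by MedDRA preferred term and group with exact 95% intervals, which covers conjunctivitis in substance.
- *That the SAE percentage is the principal safety result.* Section 13.4 leads with the preferred-term table, and neither 10.2 nor 13.4 ranks the SAE percentage first.

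**Conclusion.** The point holds as a conflict between the conjunctivitis rule in 12.3 and the definition in 12.1, which 13.4 leaves unresolved. Followed literally, it may inflate the descriptive SAE percentage and the SAE listing, probably more on dupilumab. The direction rests on sections 3.4 and 12.2. The size cannot be derived from the protocol: the range of about 3 to 15 percentage points rests on assumed conjunctivitis rates of 5% to 20% and 2% to 5%, equal true SAE rates of 2% or 4%, independence, and every conjunctivitis being non-serious and counted.

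The primary analysis, the sample size and the power are unaffected, and no planned test changes. What is at stake is a descriptive figure bearing on a stated safety objective. The change is worth making because it costs very little.

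**What to change.** 1. In 12.3, keep immediate notification of every conjunctivitis on the SAE form. Add, as the pregnancy paragraph does, that conjunctivitis meeting no 12.1 criterion is notified like an SAE and is not classed as one.
2. Record seriousness (yes/no against the 12.1 criteria) for each event in the eCRF.
3. In 13.4, or in the SAP before unblinding, restrict the SAE percentage and listing to events meeting at least one 12.1 criterion.

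A separate conjunctivitis line by arm is optional, since the preferred-term table already gives it in substance.

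The cost is one sentence in each of two sections and one eCRF item, if seriousness is not already captured there. Notification practice and patient care do not change.
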